6. PROJECT OBJECTIVES

The goal of this project is to evaluate the effectiveness of aromatherapy in air diffusion in addition to psychotropic drugs in order to evaluate a possible reduction in BPSD.

The project's hypothesis is that GROUP B patients show an improvement in their BPSD. The performed neuropsychological tests will provide the answer to the project hypotesis.

Primary objectives: validate the hypothesis that the use of aromatherapy in air diffusion can improve the BPSD management, allowing a reduce in psychotropic therapy prescribed and its secondary side effects. The patient's nurses will be tested with NPI-NH, that will characterize

frequency and seriousness of BPSD [15,16, 17]. A score greater or equal to 1 is considered positive for presence of BPSD.

Secondary objectives: validate the hypothesis that the use of aromatherapy will improve the management of BPSD patients, with a simultaneously reduction of physicians, nurses and care assistants stress. The last aspect will be evaluated with a specific part of NPI-NH test. The decrease of the initial score represented an improvement [19.20]. The NPI-NH test will be performed according to the time points defined in paragraph 7.1.1

The obtained results could be interesting to the future implementation of the use of essential oils in air diffusion in acute geriatric departments and in all facilities with BPSD patients.

7. RANDOMIZATION

Enrolled patients with BPSD will be randomized according to the following randomization scheme (AABB, ABAB, BBAA, BABA, ABBA, BAAB).

A repetition of the first 4blocks will be performed, for a total of 32 patients, 16 each group, according to the following scheme:

AABB, ABAB, BBAA, BABA AABB, ABAB, BBAA, BABA

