5. STUDY POPULATION

The population that will be evaluated within the project is constitute by patients with diagnosed dementia with BPSD (diagnosis carried out using, according to Evidence Based Medicine, the neuropsychological tests below) and/or by patients who the diagnosis of dementia with BPSD will be performed at the Geriatric Competence Centre of the Clinica Luganese Moncucco.

The enrollment will be performed in May and June 2018.

All patients mentioned above, within 48 hours after the admission at the Geriatric Department or the manifestation of BPSD, will be assessed to neuropsychological and functional tests (CAM - Confusion Assessment Method -, CDR - Clinical Dementia Rating Score -, MMSE - Mini Mental State Examination -, FAB - Frontal Assessment Battery -, scala di Tinetti, BADL - Basic Activities of Daily Living -, IADL - Instrumental Activities of Daily Living -), as required by Good Clinical Practice[18]. Subsequently, patients who can be enrolled in the study will be randomized into two groups, described below.

Here is the study population on which we will focus:

GROUP A – **controls** -: will be enrolled 16 patients eligible for criteria of inclusion, treated with psychotropic drugs.

GROUP B – aromatherapy –: will be enrolled 16 patients eligible for criteria of inclusion, treated with psychotropic drugs and aromatherapy in air-diffusion.

Based on the randomization, patients will be divided into group A - controls - and group B - aromatherapy in air diffusion.

Neuropsychiatric Inventory (NPI) is a validated and useful tool for characterizing and assessing the BPSD frequency and seriousness.

A Resident Physician will perform the NPI in our study protocol.

The physician, by interview with patient's nurse, in absence of patient himself, will fill out the NPI-NH.

The above mentioned physician, formerly operating in the Geriatric Department – who knows the geriatric assessments - and currently active in the Rheumatology Department, will therefore respect the blind study procedure.

The geriatric nurse was chosen for the close relationship of care that is created with the patient; during the test, BPSD frequency and seriousness will be evaluated.

The psychological distress induced by BPSD patients, will be evaluated on the three figures who have in charge the patient, which are nurses, care assistants and the resident physicians.

The psychological distress assessment is part of the NPI-NH test with a scale of severity from 0 to 5.

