
Nurses will be undergo to NPI – NH test within 48 hours after patient admission or at first appearance of BPSD **(T1), T2 (T1-3 days)** 3 days after enrollment, at **T3 (T1-6 days)** 6 days after enrollment, at **T4 (T1-12 days)** at 14th day. According to the same timing, NPI-NH will also be performed to the resident physicians, the nurses and the care assistants to assess the psychological distress. The NPI-NH test will be performed following the Good Clinical Practice.

The tests results performed to the two groups of patients will be considered in order to assess a possible reduction in BPSD. As the project is a pilot study, a descriptive analysis will be performed.

Here the schemes defined for treatment with aromatherapy and psychotropic drugs, according to scientific publications in the first case and scientific publications and Evidence Based Medicine in the second:

Aromatherapy

Route of administration: air diffusion with ultrasonic diffuser in a single room and for about an hour.

Doses:

- Citrus sinensis: 6 drops at 8, 12 and 18 in nebulization

and

- Lavender angustifolia: 6 drops 8 p.m. in nebulization

PRN PSYCOPHARMACOTHERAPY

Drug:

- in case of psychomotor agitation:

Haloperidol 1 mg PO 10 times in 24 hours

1 mg SC/IM 5 times in 24 hours

Reperidone 0.5mg - 2mg PO in 24 hours *Olanzapine* 2.5 mg – 5 mg PO in 24 hours

Clozapine 6.25 mg – 25 mg PO in 24 hours

Quetiapine 12.5mg - 150mg PO in 24 hours

- in case of sleep disturbance:

Valerian 1 tb - 2 tbs PO in 24 hours Melatonin 1 tb - 2 tbs PO in 24 hours Lorazepam 0.5 mg - 3mg PO in 24 hours Oxazepam 7.5mg - 45mg PO in 24 hours Clomethiazole 1 tb -3 tbs PO in 24 hours - in case of anxiety/depression: Trazodone 25 mg – 150 mg PO in 24 hours Escitalopram 10 mg – 20 mg PO in 24 hours Mirtazapine 15 mg – 45 mg PO in 24 hours

Citalopram 10 mg - 20 mg PO in 24 hours

Paroxetine 20 mg – 50 mg PO in 24 hours

The control group is treated with psychopharmacological therapy, defined by the PI, according to the Evidence Based Medicine criteria.

Patient can withdraw the ICF at any time.

The investigators could decide to withdraw a patient for safety and health.

The withdrawn patients will not be evaluated unless they have been treated for 8 days, useful to evaluate the aromatherapy efficacy.

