8. PROJECT DESIGN

The project will be managed in the acute geriatric department of the Clinica Luganese Moncucco. Enrolment and treatment scheme is present in the flow chart (chapter 2).

After randomization patients will be enrolled in the two groups GROUP A, control group, and GROUP B, treatment group.

The enrollment will be performed in 2 months.

GROUP A: 16 patients, following the inclusion criteria, will be enroll and they will be treated with psychotropic drugs.

GROUP B: 16 patients, following the inclusion criteria, will be enroll and they will be treated with psychotropic drugs and, in a complementary way, with aromatherapy in environmental diffusion.

The project hypothesis will be validated using the following neuropsychological and functional tests:

- CAM (Confusion Assessment Method);
- CDR (Clinical Dementia Rating Score)
- MMSE (Mini Mental State Examination);
- FAB (Frontal Assessment Battery);

- Tinetti's scale;
- BADL (Basic Activities of Daily Living);
- IADL (Instrumental Activities of Daily Living);
- NPI-NH (Neuropsychiatric Inventory Nursing Home Version);

Neuropsychological tests are part of clinical practice [18].

Scientific reports show that essential oils in air diffusion are effective in 3 days. A final timepoints of 14 days represent the mean hospital stay:

2 days for the collection of behavioral data;

6 days to observe the possible effectiveness of aromatherapy in air diffusion;

6 days to adapt the therapy with oils and psychotropic drugs and stabilize patient's condition for a possible discharge.

Enrolled patients and nurses will be tested according to the following times:

8.1.1 Observation for 48 hours with data collection and execution of the NPI-NH (T1): in the 48 hours after patient admission at the Geriatric Department or at the diagnosis of dementia, the information collection will be performed: sensitive data (age, gender), dementia condition (CAM, CDR, MMSE, FAB), functional status (IADL, BADL, Tinetti scale) and the used number of psychotropic drugs. As a result of this evaluation, patient will be assessed for the presence of BPSD using the NPI-NH assessment scale, nurses will be undergo to NPI – NH test within 48 hours after patient admission. In case of a score greater than or equal to 1, patient will be followed within the study project, otherwise it will follow the standard process.

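### The protocol prints the full 32-patient allocation list and describes no concealment, so each next arm can be known before the patient enters.

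*Protocol*

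**What the plan says.** Protocol Section 7 (Randomization) names the six balanced blocks of four. It then states: "A repetition of the first 4blocks will be performed, for a total of 32 patients, 16 each group, according to the following scheme". The order that follows is "AABB, ABAB, BBAA, BABA AABB, ABAB, BBAA, BABA". Section 5 (Study population) gives the key to the letters: "Based on the randomization, patients will be divided into group A - controls - and group B - aromatherapy in air diffusion". Section 19 (Additional information) describes the protocol as a working document for participating staff, not one given to patients or relatives.

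On entry, Section 5 has patients assessed "within 48 hours after the admission at the Geriatric Department or the manifestation of BPSD", with those who can be enrolled then randomised. Section 8 (Project design) says "After randomization patients will be enrolled in the two groups", and sets the threshold: "In case of a score greater than or equal to 1, patient will be followed within the study project". Section 9 allows patients whose symptoms appear later in the stay to be enrolled.

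The only masking described is in Section 5. The physician who completes the NPI-NH now works in another department and "will therefore respect the blind study procedure". Treatment is given by "air diffusion with ultrasonic diffuser in a single room and for about an hour".

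Neither the protocol text nor the SAP text supplied says who generates the list, who holds it, or how an allocation is released. The flow chart that Section 8 cites is not in the available text.

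**The concern.** Randomisation protects a comparison only if the person deciding on entry cannot foresee the arm. Here the whole order is in a document the staff hold, and no random draw is described. The sequence is the first four listed blocks in listed order, then the same four again, and two of the six listed blocks are never used.

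Some discretion over entry remains despite the 48-hour window and the score threshold. Staff can influence whether and when consent is sought, who enters first among patients in the window, how later-onset cases are taken up, and the threshold score itself, which rests on the nurse's account. If that discretion is used with the next arm in view, the arms can differ at the start.

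The direction of any bias cannot be fixed in advance. The SAP's outcome is the T3 − T1 change, and patients who are milder at T1 have less room to fall, so steering milder patients to aromatherapy could hurt that arm as easily as help it.

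The pilot label does not settle the matter. Section 13 calls the statistics purely descriptive, but Section 6 sets out to validate an efficacy hypothesis and the SAP tests the arms against each other. The SAP also reports a slightly higher CIRS comorbidity index in controls. Chance can readily produce that with 32 patients, and no size is given, so it is not evidence of selection. With a visible list, however, chance cannot simply be assumed.

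**Working it through.** **1. The plan's own figure.** Counting the printed sequence gives 8 blocks × 4 = 32 letters, 16 A and 16 B, which matches the stated totals. Positions 17–32 are identical to positions 1–16. ABBA and BAAB do not occur.

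**2. Predictability of the next arm.**
- As printed: 32 of 32 = 100%.
- Hidden list of random blocks of four, block size known, past arms visible, best guess each time. The chances of a correct guess at positions 1 to 4 are 1/2, 2/3, 2/3 and 1. They sum to 2.833 per block, so 2.833/4 = 70.8%, or 8 × 2.833 = 22.7 of 32.
- Blocks of six, same rule: 4.1/6 = 68.3%.
- Five fours and two sixes (5 × 4 + 2 × 6 = 32): (5 × 2.833 + 2 × 4.1)/32 = 22.37/32 = 69.9%.
- Simple randomisation: 50%.
- Someone who had not seen the list, but knew the block size and that the second half repeats the first, would expect 4 × 2.833 + 16 = 27.3 of 32 = 85.4%.

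**3. What selective entry could do (illustration).** The documents give no figures for this, so the inputs below are assumptions, apart from the 16 per group. There is no true effect, and tests are two-sided at 5%. In a fraction f of slots the enroller chooses between two eligible patients, with the one higher on some trait going to B and the one lower to A. The trait correlates ρ with the change score. The mean of the larger of two standard normals is 1/√π = 0.564, so

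shift between arms = 2 × 0.564 × f × ρ (in SD units).

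Example: f = 0.50, ρ = 0.5 gives 2 × 0.564 × 0.50 × 0.5 = 0.282 SD. The noncentrality is 0.282 × √(16/2) = 0.798, and with 30 degrees of freedom the rejection rate is 12.1%. The Mann-Whitney column comes from 40,000 simulated trials per cell (4.8% with no selection).

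| ρ | f | Shift (SD) | t-test, noncentral t | Mann-Whitney, simulated |
|---|---|---|---|---|
| 0.3 | 0.25 | 0.085 | 5.6% | 5.2% |
| 0.3 | 0.50 | 0.169 | 7.5% | 7.2% |
| 0.5 | 0.25 | 0.141 | 6.7% | 6.3% |
| 0.5 | 0.50 | 0.282 | 12.1% | 11.1% |
| 1.0 | 0.25 | 0.282 | 12.1% | 11.7% |
| 1.0 | 0.50 | 0.564 | 33.9% | 36.0% |

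In the last row the two columns are not like for like. Selection also narrows the spread within arms, which the noncentral t ignores; the simulated t-test there gives 37.0%.

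**4. Sensitivity to the selection model.** The table assumes that the patient passed over never enters. If that patient must take the next slot, Mann-Whitney rejection at f = 0.50 falls to about 6%, 9% and 26% for ρ = 0.3, 0.5 and 1.0. If the patient passed over instead stays available as a candidate, the rates are higher than in the table, up to about 54% in the worst case.

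**The case against.** The strongest reply is that discretion over entry is narrow. Every patient in the defined population is to be assessed within 48 hours, the threshold is a score of 1 on a total that can reach 10 × 4 × 3 = 120, and a qualifying patient is to be followed. The T1 score that opens the gate is completed by the outside physician, so his independence does some work at entry as well as in scoring. These points stand as limits. They do not close the gap, because consent and order of entry remain with people who can see the list, and the gate score still comes from the nurse's account.

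Second, the difference over the order of steps may be loose translation: Section 8 can be read as placing already eligible patients into groups. That is a fair reading, so this is a matter of wording to align, not independent evidence of a flaw.

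Third, the error rates rest on assumed inputs. At ρ = 0.3 they are near nominal, and ρ = 1.0 supposes perfect foresight of each change score. This is right, and the table shows a range, not an estimate. The selection model is not shown to be inflated, since plausible variants move the rates both ways.

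Fourth, a concealment step may sit in the missing flow chart, or the list actually used may have differed. Neither would rescue the text. A flow chart cannot hide a list printed in a staff document, and if another list was used, Section 7 is wrong and needs correcting.

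Finally, the SAP reports results in the past tense and enrolment was set for May and June 2018, so new allocation procedures may come too late. That changes the remedy, not the finding.

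**Conclusion.** The concern holds. Followed as written, Section 7 makes all 32 assignments knowable in advance, and no concealment is described in the available text. This is a fault in a stated rule, not a missing detail, and it must be fixed because the trial is presented as randomised and the arms are tested against each other.

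The predictability figures (100% as printed, about 71% for random blocks of four) follow from the printed list and simple enumeration. The error rates, 5.2% to 36.0% for the Mann-Whitney test, depend on assumed values of f and ρ and on what happens to the patient passed over. The finding is one of exposure: the documents do not show that anyone used the list, nor which way a bias would run.

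**What to change.** If any enrolment is still to come:
- Remove the sequence from Section 7.
- Have someone outside enrolment and ward care generate a computer list that keeps 16:16. The clinical research unit could do this if its independence is confirmed.
- Draw at random from all permutations of randomly mixed blocks, for example five fours and two sixes, and keep the list and block sizes out of the protocol.
- Release allocations in sequentially numbered, opaque, sealed envelopes, opened only after consent, eligibility and the T1 NPI-NH are recorded.
- State that order identically in Sections 5, 7 and 8.

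Concealing the list matters most. The room diffuser makes past arms visible on the ward, and mixing block sizes lowers predictability only from 70.8% to 69.9%, so it is a refinement. The cost is a rewritten section, one independent person and 32 envelopes, with no extra patients or visits.

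If enrolment is complete:
- State in the report that the sequence was fixed and visible to staff (or, if another list was used, what it was), and do not describe the comparison as protected by concealed randomisation.
- Show T1 NPI-NH and CIRS by arm.
- List eligible patients who were not enrolled, with reasons, if these were recorded.
- Present the CIRS-adjusted linear and median regression estimates that the SAP mentions but does not show, noting that adjustment covers measured traits only.

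This costs a disclosure statement and tables from data already held.

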8. PROJECT DESIGN

The project will be managed in the acute geriatric department of the Clinica Luganese Moncucco. Enrolment and treatment scheme is present in the flow chart (chapter 2).

After randomization patients will be enrolled in the two groups GROUP A, control group, and GROUP B, treatment group.

The enrollment will be performed in 2 months.

GROUP A: 16 patients, following the inclusion criteria, will be enroll and they will be treated with psychotropic drugs.

GROUP B: 16 patients, following the inclusion criteria, will be enroll and they will be treated with psychotropic drugs and, in a complementary way, with aromatherapy in environmental diffusion.

The project hypothesis will be validated using the following neuropsychological and functional tests:

- CAM (Confusion Assessment Method);
- CDR (Clinical Dementia Rating Score)
- MMSE (Mini Mental State Examination);
- FAB (Frontal Assessment Battery);

- Tinetti's scale;
- BADL (Basic Activities of Daily Living);
- IADL (Instrumental Activities of Daily Living);
- NPI-NH (Neuropsychiatric Inventory Nursing Home Version);

Neuropsychological tests are part of clinical practice [18].

Scientific reports show that essential oils in air diffusion are effective in 3 days. A final timepoints of 14 days represent the mean hospital stay:

2 days for the collection of behavioral data;

6 days to observe the possible effectiveness of aromatherapy in air diffusion;

6 days to adapt the therapy with oils and psychotropic drugs and stabilize patient's condition for a possible discharge.

Enrolled patients and nurses will be tested according to the following times:

8.1.1 Observation for 48 hours with data collection and execution of the NPI-NH (T1): in the 48 hours after patient admission at the Geriatric Department or at the diagnosis of dementia, the information collection will be performed: sensitive data (age, gender), dementia condition (CAM, CDR, MMSE, FAB), functional status (IADL, BADL, Tinetti scale) and the used number of psychotropic drugs. As a result of this evaluation, patient will be assessed for the presence of BPSD using the NPI-NH assessment scale, nurses will be undergo to NPI – NH test within 48 hours after patient admission. In case of a score greater than or equal to 1, patient will be followed within the study project, otherwise it will follow the standard process.

8.1.2 Assessment of NPI-NH at T2 (T1-3 days): 3 days after enrollment, patient will be re-evaluated with NPI-NH to assess BPSD progress. In addition, the distress level of on the three health caregivers is also measured with the NPI-NH test.

8.1.3 Assessment of NPI-NH at T3, assessment of vital parameters and use of drug reserves (T1-6 days): 6 days after enrollment, NPI-NH will be re-executed, with associated assessment of patient's vital signs (PAS, PAM, FC) and the use of psychotropic drug reserves.

8.1.4 Final T4 assessment (T1-12 days): NPI-NH scale will be performed in association with vital signs.

The physician in charge of dispensing the NPI-NH questionnaires to nurses to collect BPSD patients status, will also submit the questionnaires to the referring physician, nurse and care assistants with the aim to assess the level of stress in the clinical staff (see "Distress" column in NPI-NH questionnaire in the appendix).

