1. SYNOPSIS

The elderly patient demented in an acute geriatric department: pilot study, monocentric, randomized on the use of aromatherapy as a complementary treatment tool to psychopharmacology in psychological disorders and behavior (BPSD).

Rationale

Behavioral and psycological symptoms of dementia (BPSD) are a big issue for families, paramedics, physician and the patient itself (1,2,3,4).

In absence of universally recognized guidelines, the standard of treatment of these disorders involves the use of psychotropic drugs (typical/atypical neuroleptics, antidepressants, benzodiazepines) that are often found to have a reduce efficacy and induce a number of side effects such as sedation, impaired motor neurons slowdown, cardiac electrical alterations and extrapyramidal syndrome (5,6,7,8,9). In consideration of this, it is important to check for treating alternative ways, which can reduce psychological and behavioural disorders and at the same time can reduce the use of psychotropic drugs.

Concerning the aromatherapy [10], the therapeutic use of natural essential oils, there are decades of clinical experience, especially in France, accompanied by increasing scientific evidence with significant increase in publications regarding its use of psychological disorders and dementia-related behavior context (11,12,13,14).

Based on the available scientific publications, it has been therefore decided to use two essential oils (*Citrus sinensis, Lavandula angustifolia*) in environmental diffusion within the Geriatric Department of the Clinic Luganese Moncucco.

Objectives

Primary objectives: through the execution of the Neuropsychiatric Inventory – Nursing Home Version (NPI-NH), the neuropsychiatric and psychopathological symptoms of dementia patients will be evaluated in order to assess how the use of aromatherapy can improve the management of BPSD, reducing, where there is clinical indication, psychotropic therapy and secondary side effects. The score is considered positive if the presence of BPSD is greater than or equal to 1 (15, 16,17); the improvement of the score is represented from decrease of the NPI-NH respect to the initial assessment (19, 20).Performing neuropsychological tests is not an additional attention to enrolled patients, but it is part of clinical practice (18).

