4. PROTOCOL RATIONALE

Behavioral and psycological symptoms of dementia (BPSD) are a major problem for families, physicians and the patient itself [1,2,3,4].

Performing neuropsychological tests is not an additional source of distress for enlisted patients, but is part of clinical practice [18].

The standard treatment of these disorders involves the use of psychotropic drugs (typical/atypical neuroleptics, antidepressants, benzodiazepines) which are often ineffective and have a number of side effects such as sedation, reduction in cognitive performance, cardiac electrical alterations and extrapyramidal syndrome [5,6,7,8,9].

Within the scientific community, it is therefore mandatory to identify alternative ways of managing BPSDs, which can have a beneficial effect on patient life and, at the same time, a reduction in the used of psychotropic drugs.

The therapeutic use of natural essential oils has decades of clinical experience, especially in France, accompanied by an increase numbers of publications in their use in BPSD [11,12,13,14].

The knowledge of alternative treatments of BPSD (such as aromatherapy) are the basis of our study project, which involves the introduction of essential oils in the BPSD management, while maintaining conventional psychotropic therapy (typical/atypical neuroleptics, antidepressants, benzodiazepines) in a prefixed form of ProReNata (PRN) (paragraph 5).

The identified oils (*Citrus sinensis, Lavender angustifolia*) were selected on the degree of purity defined by the mass spectrophotometry available by the supplier.999

The choice of adjuvant therapy with essential oils could allow, in accordance with the 3rd principle of Medical Ethics to administer natural treatment to patients with distress with BPSD reducing, if possible, use of psychotropic drugs and their major side effects.

The use of essential oils in treatment of BPSD can also have a positive impact on patient economic management due to limited costs, allowing a distribution of treatments according to IV Principle of Ethics Medical: principle of justice.

Mild Cognitive Impairment (MCI) patients were excluded from the protocol as a form of predementia.[21].

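### Lower psychotropic use is part of the primary objective, but the visit text lists no drug-use measure in the same form at baseline and follow-up, and none at T4

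*Protocol*

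**What the plan says.** Both statements of the primary objective mention drug reduction. The Synopsis speaks of "reducing, where there is clinical indication, psychotropic therapy and secondary side effects", and section 6 of "allowing a reduce in psychotropic therapy prescribed and its secondary side effects". Section 12 presents lower psychotropic use as the patient's benefit if the oils work.

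The drug data are set out by visit in section 8. The baseline collection (8.1.1) ends with "and the used number of psychotropic drugs". T2 (8.1.2) has the NPI-NH and staff distress. T3 (8.1.3) adds vital signs "and the use of psychotropic drug reserves". For T4, section 8.1.4 says only that the "NPI-NH scale will be performed in association with vital signs". The same section divides the stay into periods, the last being "6 days to adapt the therapy with oils and psychotropic drugs".

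Section 13 calls the statistics descriptive and names no variable. The SAP's Statistical methodology section compares T3 − T1 score changes between the arms, with a regression adjusting for the initial CIRS index. It names no drug-use variable.

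**The concern.** The oils are added to drug therapy that the ward can adjust. A result with similar NPI-NH scores in both arms but less medication in the aromatherapy arm would count in favour of the oils under the stated objective. With the listed data, that could appear only as a difference in reserve use at T3. The data would not show whether therapy fell from its starting level. They would also not show where it stood after the period in which it was meant to be adapted. The T1 and T3 items are different quantities, and neither says what is counted or over how many hours. Two people filling in the form could therefore record different things.

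**Working it through.** The check is a comparison of texts; the plan gives no figure to reproduce.

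**Drug-use items by visit (sections 8.1.1 to 8.1.4)**

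| Visit | Timing | Drug-use item listed | Unit or window |
|---|---|---|---|
| T1 | within 48 hours | number of psychotropic drugs | not stated |
| T2 | 3 days after enrolment | none | – |
| T3 | 6 days after enrolment | use of psychotropic reserves | not stated |
| T4 | T1 + 12 days | none | – |

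Visits with a drug item: 2 of 4. Baseline and follow-up pairs with the same stated measure: 0. Drug items after T3: 0.

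**Where the adaptation period falls.** Section 8 divides the stay into 2 + 6 + 6 = 14 days: observation, effectiveness, adaptation. If enrolment is taken at the end of the 2 observation days, T3 is at day 2 + 6 = 8, the end of the effectiveness period. T4 is then at day 2 + 12 = 14, the end of the adaptation period. This agrees with section 5, which puts T4 at the 14th day. The adaptation period thus lies between T3 and T4, and the visit that closes it lists no drug item.

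**What the listed items can answer**

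- Do the arms differ in reserve use at T3? Yes, once a unit and window are fixed.
- Do the arms start alike? Only coarsely, from the T1 number of drugs.
- Did drug use change from baseline? No: the two items are not the same quantity.
- What was drug use at the end of the adaptation period? No item is listed.

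**How a T1 value should be used.** Suppose the arms differ at T1 by d, in SD units, through chance. Take equal SDs at both visits, a T1–T3 correlation r, and no treatment effect.

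- Expected raw difference at T3: r × d.
- Expected difference in raw change: r × d − d = (r − 1) × d.
- Expected difference at T3 adjusted for T1: r × d − r × d = 0.

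A raw change therefore does not remove a chance imbalance; it reverses its sign. At r = 0.5 the two unadjusted results are equal in size, +0.5d and −0.5d. The documents give neither d nor r, so this supports the choice of method and does not estimate an error in this trial.

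**Choice of measure.** Section 5 lists 15 drugs: 5 for agitation, 5 for sleep, 5 for anxiety or depression. Their doses cannot be added without an equivalence rule, which the plan does not contain. Counts by class avoid that problem.

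**The case against.** **The objective is conditional.** Section 6 states the goal and the hypothesis in terms of BPSD and expects the neuropsychological tests to give the answer. Improvement relative to the initial assessment is defined for the NPI-NH only. This stands: a reader might infer a co-primary drug endpoint left without data, and the documents do not support that. Still, drug reduction appears under the primary objectives in both places, and none of the tests listed in section 8 measures it.

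**Randomisation makes the T3 comparison valid.** This also stands. A reader might infer that reserve use at T3 is biased or unusable without a matching baseline. It is not: the comparison is valid on average. What it lacks is a description of change and a like-for-like look at the starting level.

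**Therapy is given in preset PRN form (section 4), so reserves may cover most of it.** This is partly right, and the T1 item may concern the same drugs. A number of drugs and an undefined use of reserves remain different measures, and section 6 refers to therapy prescribed, which may be wider than PRN.

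**The visit text may not be complete.** The SAP uses a CIRS index that section 8.1.1 does not list. The chapter 2 flow chart and part of the SAP were not available for this check. The finding is therefore confined to sections 8.1.1 to 8.1.4 and the available SAP text.

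**It is a descriptive pilot of 32 patients.** True, but a description of change also needs the same measure twice.

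**Conclusion.** The point holds in a limited form. A drug item is listed at 2 of 4 visits, with no measure repeated and none at T4. Following the visit text as written leaves the drug-reduction part of the primary objective answerable only as a difference between arms in reserve use at T3.

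Two stronger readings should be avoided. A reader might infer that half of the 12 days from T1 to T4 has no drug data. That share cannot be derived, because the T3 item has no stated window and the days it covers are unknown. A reader might also infer that the NPI-NH result is biased. No size or direction of such a bias follows from the documents, and the SAP's T3 − T1 score comparison is not affected by the absence of drug data after T3.

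The conclusion assumes that the flow chart and the unavailable part of the SAP add no drug-use item. It is a worthwhile, inexpensive improvement and changes no sample-size or power figure.

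**What to change.** In both arms, at T1, T3 and T4, take from the ward drug chart:

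- the number of regular psychotropic drugs;
- the number of PRN psychotropic administrations per 24 hours, by class (agitation, sleep, anxiety/depression).

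State the window. At T1 it should run from admission or BPSD onset to T1, since T1 may come before 48 hours of ward chart exist. At T3 and T4 it could be the preceding 48 hours. A rate per 24 hours keeps windows of unequal length comparable.

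Add to the SAP one descriptive table of these measures by arm and visit, beside the NPI-NH results, and keep the T3 comparison of reserve use. If a between-arm estimate is given at T3 or T4, adjust it for the T1 value and do not rely on the raw change.

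The cost is chart transcription for 32 × 3 = 96 patient-visits, each of which may hold several drugs, plus one table. No extra patient test or visit is needed, in keeping with the protocol's commitment on additional tests. Counts will miss a dose reduction within the same drug; that is the price of not needing an equivalence rule.

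If the flow chart or the rest of the SAP already plans this, state only the unit and window.
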